13.1.2.3 Sensitivity Analysis Using Randomized Analysis Set

This sensitivity analysis using MI assuming MAR will be performed using the Randomized Analysis Set.

13.1.2.4 Remote Assessments

To assess the impact of the intercurrent events of remote assessments on the primary analysis, an indicator variable will be assigned to flag subjects that had assessments done remotely for the primary efficacy endpoint at any visit including baseline (Yes/No). The remote visit flag indicator variable and the interaction between treatment group and remote visit flag indicator variable will be included as factors in the MMRM mode.

13.2 Secondary and Exploratory Efficacy Analyses

The change from Baseline at each post-baseline timepoint in the ABC subscale scores (lethargy, stereotypic behavior, hyperactivity, inappropriate speech), the CGI-S of irritability score and the CGI-I of irritability score will be analyzed using an MMRM model similar to the primary analysis described above for the primary endpoint, except that the Baseline covariate of the endpoint being analyzed will be included in the model instead of the Baseline ABC-I subscale score. For CGI-I of irritability score, the Baseline covariate include in the MMRM model will be the Baseline CGI-S of irritability score

The change from Baseline at each post-baseline timepoint in the RBS-R scores, the VABS-Socialization subscale score, and the CGSQ scores will be analyzed using an MMRM model similar to the primary analysis described above for the primary endpoint, except that the Baseline value of the endpoint being analyzed will be included in the model instead of the Baseline ABC-I subscale score, also the visit variable included in the model will reflect the visits scheduled for the respective endpoints.

The proportion of subjects with ≥25% reduction in the ABC-I subscale score, the proportion of subjects with a CGI-I of irritability score of 1 or 2, and the proportion of subjects with ≥25% reduction in the ABC-I subscale score and a CGI-I of irritability score of 1 or 2 will be summarized at each post-Baseline timepoint. The proportions will be compared between each pimavanserin dose group and the placebo group using Cochran-Mantel-Haenszel test stratified by age group and region; Newcombe's 95% CI stratified by age group and region will be presented. Subjects with missing score at a given visit are considered as non-responders for that visit.

In addition to the treatment comparisons for the Week 6 timepoint, the treatment groups will also be compared at each of the other timepoints (Weeks 1, 2, 3, 4, or 5). These comparisons will be considered exploratory.

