9.4 Population Analysis Sets

The **Safety Analysis Set** will include all randomized subjects who received at least one dose of study drug (pimavanserin or placebo). Subjects will be analyzed based on the treatment that they actually received. The Safety Analysis Set will be used for all safety analyses.

The **Full Analysis Set** will include all randomized subjects who received at least one dose of study drug and who have both a baseline value and at least one post-Baseline value for the ABC-I subscale score. Subjects will be analyzed based on their randomized treatment. The Full Analysis Set will be used for the analysis of all efficacy endpoints.

The **Pharmacokinetics Analysis Set** will include subjects in the Safety Analysis Set with at least one measurable plasma concentration. The Pharmacokinetics Analysis Set will be used for pimavanserin and AC-279 plasma concentration summaries.

Any other analysis sets, if necessary, will be defined in the SAP.

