4 ANALYSIS SETS

Randomized Analysis Set

The Randomized Analysis Set will include all unique subjects who were randomized. Subjects will be analyzed based on their randomized treatment.

Safety Analysis Set

The Safety Analysis Set will include all randomized subjects who received at least one dose of study drug (pimavanserin or placebo). Subjects will be analyzed based on the treatment that they actually received. If a subject received wrong kit, the actual treatment group will be determined based on the majority of treatment the subject received. The Safety Analysis Set will be used for all safety analyses.

Full Analysis Set

The Full Analysis Set will include all randomized subjects who received at least one dose of study drug and who have both a baseline value and at least one post-baseline value for the ABC-I subscale score. Subjects will be analyzed based on their randomized treatment. The Full Analysis Set will be used for the analysis of all efficacy endpoints.

Pharmacokinetics Analysis Set

The Pharmacokinetics Analysis Set will include subjects in the Safety Analysis Set with at least one measurable plasma concentration. The Pharmacokinetics Analysis Set will be used for pimavanserin and AC-279 plasma concentration summaries.

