5.2.1 Aberrant Behavior Checklist

The Aberrant Behavior Checklist (ABC) is a parent/caregiver-rated scale comprised of five empirically-derived subscales encompassing 58 items that describe various behavior problems (Aman et al. 1985; Kaat et al. 2014). The subscales have been labeled:

- I. Irritability (irritability, agitation, and crying) (15 items)
- II. Lethargy (lethargy and social withdrawal) (16 items)
- III. Stereotypic Behavior (7 items)

- IV. Hyperactivity (hyperactivity and noncompliance) (16 items)
- V. Inappropriate Speech (4 items)

The ABC will be administered at Screening and Baseline, and at all post-baseline visits from Week 1 through Week 6. Items are rated on a 4-point Likert scale ranging from 0 (not at all a problem) to 3 (the problem is severe), with higher scores indicating more severe problems. Subscale scores are calculated by summing the items within that subscale.

Missing ABC item scores will not be imputed. If any item is missing within a subscale, then that particular subscale score will be missing.

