12 EFFICACY ANALYSIS CONSIDERATIONS

All efficacy analyses will be performed using the planned treatment assignments based on the randomization schedule for the Full Analysis Set.

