13.1.2 Sensitivity Analysis

The following sensitivity analyses of the primary efficacy endpoint are planned to account for intercurrent events.

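### The missing-equals-non-responder rule applies only inside the Full Analysis Set, so subjects with no valid post-baseline ABC-I drop out of all three responder analyses instead of counting as failures

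*SAP*

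**What the plan says.** The missing-data rule for the responder endpoints is in SAP 13.2: "Subjects with missing score at a given visit are considered as non-responders for that visit". That section names no population of its own. The population comes from two other places. SAP 4 says: "The Full Analysis Set will be used for the analysis of all efficacy endpoints". SAP 12 says: "All efficacy analyses will be performed using the planned treatment assignments based on the randomization schedule for the Full Analysis Set".

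Entry to the FAS is limited to randomised, dosed subjects "who have both a baseline value and at least one post-baseline value for the ABC-I subscale score". Protocol 9.4 has the same condition. SAP 5.2.1 makes it stricter than it first appears: "If any item is missing within a subscale, then that particular subscale score will be missing".

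The SAP plans one efficacy analysis on everyone randomised, in 13.1.2.3: "This sensitivity analysis using MI assuming MAR will be performed using the Randomized Analysis Set". It falls under SAP 13.1.2, whose scope is set by its opening sentence: "The following sensitivity analyses of the primary efficacy endpoint are planned to account for intercurrent events". The SAP addendum changes only the testing order and the tipping-point analysis.

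**The concern.** A likelihood-based MMRM on observed cases has a natural reason to require a post-baseline score, because a subject without one contributes no outcome. That reason disappears once a missing value is defined as failure. The outcome is then known for every subject, and the strata of the Cochran-Mantel-Haenszel (CMH) test, age group and region, are fixed at randomisation. The version history in SAP 21.4 lists the non-responder rule as a Version 3.0 change; the FAS condition was left in place.

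The result is an exclusion based on something that happens after randomisation. If it falls unequally on the arms, the responder differences, their CMH tests and their Newcombe intervals are distorted. The CGI-I endpoint is caught as well: a subject with a recorded CGI-I but no complete post-baseline ABC-I is removed from an analysis that does not need the ABC-I.

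**Working it through.** **Three subjects traced through the rules.** All three are randomised and dosed, and none has a Week 6 score.

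- A stops on Day 4 and completes the ABC-I in full at an early-termination (ET) visit. SAP 5.3.3 lets ET data enter the visit windows, and the Week 1 window in SAP 5.3.2 runs from Day 2 to Day 11. A is in the FAS and is a Week 6 non-responder.
- B stops on Day 4 and has no ET assessment. B has no post-baseline ABC-I, is outside the FAS and appears nowhere.
- C attends Week 1, has a CGI-I recorded, leaves one ABC-I irritability item blank, and then drops out. Under SAP 5.2.1 the ABC-I is missing, so C is outside the FAS and is lost from all three endpoints, including the observed Week 1 CGI-I.

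A, B and C have the same Week 6 status but are treated differently.

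**The plan's own figure.** The documents give no figure for the responder endpoints. The sample size in SAP 3.5 supplies only the arm size, and it reproduces: a difference of 5, SD 10 and 64 per group give power 0.801 by two-sided t-test at 0.05; 64/0.85 = 75.3, rounded up to 76; 3 × 76 = 228.

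**Size, fixing the FAS rates.** Assume FAS response of 50% on active and 35% on placebo, with 3% or 5% of active and 1% of placebo subjects lacking any valid post-baseline ABC-I. Rate among all randomised = FAS rate × (1 − proportion lost).

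- 3% vs 1%: 0.50 × 0.97 − 0.35 × 0.99 = 0.4850 − 0.3465 = 0.1385
- 5% vs 1%: 0.50 × 0.95 − 0.35 × 0.99 = 0.4750 − 0.3465 = 0.1285
- FAS: 0.50 − 0.35 = 0.1500

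The overstatement is 1.15 to 2.15 points. The standard error of the difference with 76 per arm is √[(0.50 × 0.50 + 0.35 × 0.65)/76] = 0.079, or 7.9 points. The shift is therefore about 0.15 to 0.27 standard errors.

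**Size, fixing the counts.** Assume 38 of 76 responders on active and 27 of 76 on placebo when everyone randomised is counted. If k subjects are excluded from an arm, the FAS rate is r/(76 − k), which is the all-randomised rate × 76/(76 − k). That factor is 1.027 for k = 2 and 1.056 for k = 4. The p-values are from an unstratified chi-square test, because stratum counts are not available.

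| Excluded, active / placebo | Active | Placebo | Difference (points) | p |
|---|---|---|---|---|
| 0 / 0 (all randomised) | 50.0% | 35.5% | 14.5 | 0.0713 |
| 2 / 2 | 51.4% | 36.5% | 14.9 | 0.0685 |
| 4 / 2 | 52.8% | 36.5% | 16.3 | 0.0477 |
| 4 / 0 | 52.8% | 35.5% | 17.3 | 0.0345 |

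With the imbalance reversed (0 / 4), the difference is 38/76 − 27/72 = 50.0% − 37.5% = 12.5 points, so the FAS then understates the effect. As an outer limit, suppose the whole planned 15% discontinuation (11 of 76) lacks a valid post-baseline ABC-I, on active only: 22.9 points, p = 0.0065. That is a bound and not an expectation.

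**The case against.** The strongest reply is that few subjects are affected. Protocol 4.5.1 asks sites to obtain the ET visit after early discontinuation, the ABC is scheduled there, and Protocol 6.9 allows off-site, video or telephone assessment in some circumstances. A subject who stops for intolerance in the first week and completes that assessment behaves like subject A. This stands. A reader might infer that early dropouts as a group are deleted; the documents do not support that, because only those with no valid post-baseline ABC-I at all are lost.

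A reader might also infer a bias in favour of pimavanserin. That holds only if such losses are more frequent on active drug. The completion figures in Protocol 1.3.1 do not settle it: 87.9% on pimavanserin against 96.0% on placebo in the 6-week adult schizophrenia study, but 85.6% against 86.1% in the 26-week one. Both are adult studies, and both figures count all discontinuation, not loss before a first score.

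The loss is also visible. SAP 6 reports FAS numbers by arm and lists each excluded subject with reasons. For the ABC-I and composite endpoints, excluded subjects would add no responders, so a reader can recompute crude rates with the randomised denominator. That does not give the stratified test or interval. It also fails for the CGI-I endpoint, where an excluded subject may have an observed favourable score.

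Finally, the FAS is the protocol's stated population for efficacy. That is true, and it means the change has to be documented as a departure.

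**Conclusion.** The point holds within limits. SAP 4, 12 and 13.2 together drop subjects without a valid post-baseline ABC-I from all three responder analyses, although the SAP's own rule defines a missing score as failure. Nothing elsewhere in the SAP or its addendum restores them.

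The effect is likely to be modest: about 1 to 2 points on the risk difference under assumed FAS rates of 50% and 35% and losses of 3-5% against 1%, close to nil if losses are equal, and of opposite sign if placebo loses more. The documents give neither response rates nor the expected number without a valid post-baseline score, so all these inputs are assumptions. With 76 per arm, a net imbalance of two to four subjects can still carry a nominal p-value across 0.05, as the count-based table shows.

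It would be wrong to infer that the trial's main result is at risk. The responder endpoints are secondary and outside the testing hierarchy in SAP 12.4 and the addendum, so the primary conclusion and Type I error control do not depend on them. They are still prespecified comparisons with tests and intervals, and an avoidable post-randomisation exclusion should be removed from them.

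**What to change.** In SAP 13.2, run the CMH tests and stratified Newcombe intervals for the three responder endpoints on all randomised subjects. Use either the Randomized Analysis Set already defined in SAP 4 or, if undosed subjects are not wanted, all randomised and dosed subjects. Make this the main responder analysis, or prespecify it beside the FAS version.

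State the scoring rule by endpoint: a subject is a non-responder at a visit when the score that endpoint needs is missing at that visit. An observed CGI-I is then used for the CGI-I endpoint even if the ABC-I is missing, while the composite needs both.

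Record the change in SAP 19, which currently declares no changes from the protocol, because Protocol 9.4 assigns all efficacy endpoints to the FAS. No new data or imputation model is needed. The costs are slightly lower response rates and a documented departure from the protocol's FAS rule.

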14 SAFETY ANALYSES

The safety analysis will be performed on the Safety Analysis Set based on the actual treatment received. Safety results will be summarized by treatment group using descriptive statistics. No formal statistical testing will be performed for any of the safety endpoints.

Circumstances may arise (e.g., pandemic, natural disaster, political upheaval, or technical issues) when on-site assessments of safety measures may not be possible. In those cases, assessments may be performed at the subject's place of residence either in person or via video technology or telephone, where possible. If a subject is unable to come to the site for lab draws and the site is unable to travel to the subject's place of residence, the subject may visit a local lab to obtain all safety labs. The Investigator must contact the Medical Monitor for approval with the plan. Sites must keep a log to identify details of all visits that are administered remotely.

14.1 Adverse Events

All Adverse events (AEs) will be coded using MedDRA version 24.0 or higher.

An AE (classified by preferred term) will be considered a treatment-emergent AE (TEAE) if it starts after the first study dose administration and no later than last study dose date + 30 days. AEs reported on Day 1 based on Baseline (pre-dose) findings (e.g. clinically significantly abnormal vital signs, laboratory test results, or electrocardiogram parameters) will not be considered as TEAEs.

The event counts and the number and percentage of subjects reporting TEAEs in each treatment group, and the two pimavanserin groups combined will be tabulated by SOC and preferred term; and, by SOC, preferred term, and maximum severity. If more than one AE occurs with the same preferred term for the same subject, the subject will be counted only once for that preferred term using the most severe and more related occurrence for the summarization by severity and by relationship to study drug, respectively. The display in these tables will be sorted alphabetically by SOC, and then by frequency of the two pimavanserin groups combined within each SOC.

The event counts and the number and percentage of subjects with any TEAEs will also be tabulated by preferred term without SOCs within each treatment group and sorted by frequency of the two pimavanserin groups combined.

The incidence of most frequently reported (preferred terms reported by $\geq 5\%$ of subjects in any treatment group) TEAEs, TEAEs leading to discontinuation, TEAEs related to study drug, TEAEs by maximum severity, fatal TEAEs (i.e., events that cause death), serious TEAEs, and serious TEAEs related to study drug, will be summarized by SOC, preferred term, and treatment group. In addition, TEAEs by SOC, preferred term, and stimulant use will be summarized.

Version 3.0

29 July 2024

The relationship of selected AEs to COVID-19 will be assessed as detailed in the GSD and provided in the listing. Additional summaries of relationship to COVID-19 may be provided.

An AE listing by subject will display all events, including those which are not treatment-emergent, and will include the verbatim term in addition to the MedDRA SOC and preferred term. This listing will also include all relevant eCRF data associated with the event: e.g. date of onset, date resolved, date of last dose, severity, frequency, outcome, relationship to study drug, action taken with study drug, and required therapy. When a date is presented, the study day associated with the date will also be displayed. Separate listings will be provided for TEAEs leading to discontinuation, TEAEs related to study drug, SAEs, and fatal AEs.

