3.1.3 Safety Follow-up Period (30 Days)

Subjects who successfully complete the 6-week Treatment Period may enroll in a 52-week, open-label extension study (Study ACP-103-070) if they qualify and if the subjects have presented to the clinic in person to sign the ACP-103-070 informed consent form (ICF) and have all ACP-103-069 end-of-treatment procedures. For subjects who discontinue treatment prematurely from the study or who do not enroll in the extension study (Study ACP-103-070), in addition to the EOT or ET visit performed at time of discontinuation, a safety follow-up telephone call will occur 30(+3) days after the last dose of

study drug. Those who roll over into the 52-week open-label extension study, or have withdrawn consent to participate in all parts of the study, or who have well documented "lost to follow-up" status will be exempt. For subjects who discontinue prematurely or who do not continue into the extension study, the Investigator must ensure that the subject is appropriately transitioned to standard of care and/or followed for additional care per the Investigator or physician's clinical judgment.

The schedule of assessments is provided in Table S–1.

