7 ADVERSE EVENTS

7.1 **Specification of Safety Parameters**

7.1.1 **Definition of Adverse Event**

An AE is defined as "any untoward medical occurrence in a patient or clinical study participant, temporally associated with the use of study drug, whether or not considered related to study drug".

An AE can therefore be any unfavorable and unintended sign (e.g., an abnormal laboratory finding), symptom, or disease temporally associated with the use of a drug, without any judgment about causality or seriousness. An AE can arise from any use of the drug (e.g., off-label use, use in combination with another drug) and from any route of administration, formulation, or dose, including an overdose.

A suspected adverse reaction is any AE for which there is a reasonable possibility that the drug caused the AE.

AEs do not include the following:

Stable or intermittent chronic conditions (such as myopia requiring eyeglasses) that are present prior to Baseline and do not worsen during the study

 Medical or surgical procedures (e.g., surgery, endoscopy, tooth extraction, transfusion) or scheduled surgery/procedure. The condition that leads to the procedure is an AE if not present at time of consent.

- Overdose of concomitant medication without any signs or symptoms will not be considered an AE, but if a subject is hospitalized or has other serious criteria, the overdose will be considered an AE and shall be reported on the Sponsor's Overdose Reporting form.
- Hospitalization for elective surgery planned prior to study (situation where an untoward medical occurrence has not occurred)
- Pregnancy will not be considered an AE, but if it occurs, it will be reported on a pregnancy form

For subjects who enroll into the open-label extension study, AEs will be recorded from the time informed consent is obtained in the present study until the first dose of study drug in the open-label study.

For subjects who discontinue from the study or do not enroll into the open-label extension, AEs will be recorded from the time informed consent is obtained until 30 days after the last dose of study drug.

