9.5.3.1 Treatment-emergent Adverse Events

All AEs will be coded using the Medical Dictionary for Regulatory Activities (MedDRA) coding dictionary. All AEs will be listed and treatment-emergent adverse events (TEAEs) will be summarized by system organ class and preferred term. A TEAE is defined as an AE that started after first study dose administration and no later than last study dose date + 30 days. TEAEs leading to discontinuation, TEAEs related to study drug, TEAEs by maximum severity, fatal TEAEs, serious TEAEs, and serious TEAEs related to study drug will also be summarized.

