3 STUDY DESIGN

3.1 General Study Design

This study will be conducted as a 6-week, randomized, double-blind, fixed-dose, placebo-controlled, parallel group study in children and adolescents (5 through 17 years of age) with irritability, agitation, or self-injurious behaviors associated to ASD. Approximately 60 global sites and eight countries will participate in this study.

The study will have three periods:

[figure not shown]
• Screening period: 3-28 days

• Double-blind treatment period: 6 weeks

• Safety follow-up period: 30 (+3) days for those subjects who discontinue prematurely from the study or who do not enroll in the 52-week, open-label extension study (Study ACP-103-070)

The study design schematic is provided in Figure 1.

Figure 1 Schematic of Study Design

Abbreviations: ASD=autism spectrum disorder; EOT=end of treatment; ET=early termination; yrs=years

Subjects who complete the 6-week Treatment Period may be eligible to enroll in a 52-week, open-label extension study (Study ACP-103-070). Subjects entering ACP-103-070 will not complete a follow-up telephone call as they will be immediately enrolled in ACP-103-070.

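### TEAE tables use one cutoff of last dose + 30 days, but AE recording stops at the first open-label dose for rollover subjects, so crude percentages mix unequal observation times

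*SAP*

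**What the plan says.** The counting rule is the same for everyone. SAP 14.1 treats an event as a TEAE "if it starts after the first study dose administration and no later than last study dose date + 30 days", and Protocol 9.5.3.1 agrees: "A TEAE is defined as an AE that started after first study dose administration and no later than last study dose date + 30 days".

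The recording rule is not the same for everyone. Under Protocol 7.1.1, events in subjects who enter the extension are recorded from consent "in the present study until the first dose of study drug in the open-label study". For subjects who discontinue or do not enter it, "AEs will be recorded from the time informed consent is obtained until 30 days after the last dose of study drug".

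Rollover leaves almost no gap. SAP 3.1 states: "Subjects entering ACP-103-070 will not complete a follow-up telephone call as they will be immediately enrolled in ACP-103-070". It is open only to completers. Protocol 3.1.3 says: "Subjects who successfully complete the 6-week Treatment Period may enroll in a 52-week, open-label extension study (Study ACP-103-070) if they qualify". The same section exempts some subjects from the 30-day call: "Those who roll over into the 52-week open-label extension study, or have withdrawn consent to participate in all parts of the study", together with documented losses to follow-up.

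SAP 14.1 reports event counts and subject percentages by arm on the Safety Analysis Set. It plans no on-treatment table, no person-time rate and no split by rollover status. It also does not say how an event is treated if it starts in the extension within 30 days of the last double-blind dose.

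**The concern.** The last 30 days of the TEAE window are nearly empty for rollover subjects and filled for most others, yet both share one denominator per arm. Who falls in which group is settled after randomisation, by completing, qualifying and agreeing to continue. All three can depend on tolerability or lack of effect. A subject who leaves must be "appropriately transitioned to standard of care and/or followed for additional care per the Investigator or physician's clinical judgment", and under Protocol 4.8.2.1 the medication restrictions end at Visit 8/ET. Events in those days are therefore observed under different conditions but tabulated under the randomised arm.

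At stake is the drug-placebo comparison of TEAE percentages, which is central to the tolerability objective. Low-frequency terms are sensitive: with 76 per arm, a preferred term enters the table of terms reported by at least 5% of subjects at 4 subjects (4/76 = 5.3%) but not at 3 (3/76 = 3.9%).

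**Working it through.** The documents give no figure for this effect, so there is none to reproduce.

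**Inputs from the documents**
- Week 6 target day: 43 (SAP Table 1).
- Counting limit: last dose + 30 days (SAP 14.1).
- Recording limits: Protocol 7.1.1, as above.

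**Observation time**
- Rollover completer: about 43 days.
- Completer who does not roll over: 43 + 30 = about 73 days.
- Subject stopping on day d: d + 30 days. Day 8 gives 38, Day 21 gives 51.

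A subject stopping before about Day 13 (43 − 30) is observed for less time in total than a rollover completer, but most of that time is off dosing (30 of 38 days, 79%, for Day 8).

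**Assumed inputs (not in the documents)**
- The same true risk in both arms and a constant event rate, with p = 50% having any TEAE by Day 43.
- Non-rollover of 20% in one arm and 40% in the other.

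**Formula**

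λ = −ln(1 − p)/43, and P(t) = 1 − exp(−λt).

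For p = 0.5: λ = 0.01612, P(43) = 0.500, P(51) = 0.560, P(73) = 0.692.

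**Case A: all non-rollover subjects are completers**
- 20% arm: 0.8 × 0.500 + 0.2 × 0.692 = 53.8%
- 40% arm: 0.6 × 0.500 + 0.4 × 0.692 = 57.7%
- Spurious difference: about 3.8 points (unrounded).

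**Case B: all non-rollover subjects stop on Day 21**
- 20% arm: 0.8 × 0.500 + 0.2 × 0.560 = 51.2%
- 40% arm: 0.6 × 0.500 + 0.4 × 0.560 = 52.4%
- Spurious difference: 1.2 points.

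**Sensitivity**
- Case A with p = 0.3: 33.1% versus 36.2%, or 3.1 points.
- Case A with 25% versus 35% non-rollover: 1.5 points (p = 0.3) to 1.9 points (p = 0.5).
- Off-drug events arise or are captured at half the on-drug rate, so 30 days count as 15. Case A becomes 0.2 × [P(58) − P(43)] = 0.2 × (0.607 − 0.500) = 2.1 points. Case B becomes 0.2 × [P(36) − P(43)] = 0.2 × (0.440 − 0.500) = −1.2 points, so the sign reverses.
- Equal rollover and discontinuation patterns: 0 points between arms, although each arm's percentage still depends on its mix.

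**Why an on-treatment cut alone is not enough**

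Cutting at last dose gives a Day 21 stopper P(21) = 0.287. The crude percentages in Case B become 0.8 × 0.500 + 0.2 × 0.287 = 45.7% and 0.6 × 0.500 + 0.4 × 0.287 = 41.5%, a 4.3-point difference (unrounded) in the other direction. Person-time rates are needed alongside the cut.

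**Is imbalance plausible?**

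Protocol 1.3.1 reports two earlier adult schizophrenia trials. In the 6-week trial 96.0% completed on placebo and 87.9% on pimavanserin, a gap of 8.1 points. In the 26-week trial the figures were 86.1% and 85.6%. Imbalance is possible but not established.

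**The case against.** The other side has several good points, and most of them limit the size rather than remove the issue.

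- **The window is defensible.** It is the protocol's own definition. Protocol 1.3.2 gives half-lives of 57 h (parent) and 200 h (AC-279), so five half-lives are 5 × 57/24 = 11.9 days and 5 × 200/24 = 41.7 days. Off drug means no dosing, not no exposure. This stands; the difficulty is only that the window is filled for some subjects and not others.
- **Not everyone else has 30 more days.** A reader might infer that every non-rollover subject contributes 73 days. Only completers who do not roll over can. Full consent withdrawals and documented losses to follow-up are exempt from the call.
- **AE dropouts do not raise the any-TEAE percentage.** A subject who stops for a treatment-emergent event is already counted. Further days can add only to term-level percentages and event counts.
- **Follow-up captures less.** Protocol 6.7 provides one telephone contact on medications, AEs, syncope and somnolence. No weight, laboratory test or ECG is scheduled. The constant-rate figures therefore probably overstate the effect.
- **New antipsychotics are conjecture.** Protocol 1.1.2 names two approved drugs with prominent weight and metabolic effects, so a reader might infer that their events will be counted against the randomised arm. The plan says only that subjects move to standard of care, and this follow-up is poorly placed to detect such effects.
- **The data are not hidden.** Listings carry onset and last-dose dates (SAP 14.1), and post-treatment medications are summarised separately (SAP 11). That permits reconstruction, but it does not correct the summary tables.
- **The effect is small against sampling error.** With 76 per arm and percentages near 50%, the standard error of a difference is √(2 × 0.25/76) = 8.1 points. This is true, but a predictable distortion is still worth removing when it is cheap to do so.

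**Conclusion.** The point holds in limited form. One counting limit is applied to subjects whose events are recorded for different lengths of time, and which length applies is decided after randomisation. The crude TEAE counts and percentages depend on that mix. The arm contrast is distorted only if rollover or discontinuation differs by arm.

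Under the stated assumptions the spurious difference is about 1.2 to 3.8 points for 20% versus 40% non-rollover. It is smaller with a milder imbalance, and its sign can reverse when stopping is early and off-drug events are fewer or less well captured. Base rate, rollover shares and stopping times are all assumptions, because the documents give none.

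A reader might infer that the safety conclusions are invalid or that an error rate is compromised. The documents do not support that: SAP 14 makes safety descriptive with no formal testing. This is a cheap improvement, not a required correction.

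**What to change.** 1. Keep the TEAE tables as the protocol defines them.
2. Add to SAP 14.1 an on-treatment set (overall, by severity, related, serious) limited to onset after first dose through the last double-blind dose date. Use that single cut for every subject.
3. In that set, give exposure-adjusted rates per person-time beside the percentages, because early stoppers have less time on drug.
4. Tabulate events from then to last dose + 30 days separately, by rollover status, with a flag for psychotropics newly started after treatment, taken from the post-treatment medication category in SAP 11.
5. State in one sentence whether extension-study events starting within 30 days of the last double-blind dose enter any of these tables.

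The cost is some SAP wording and one extra set of outputs from data already collected. The drawback is that late-onset events do not appear in the on-treatment table; they remain visible in the protocol-defined and post-treatment tables.
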